#### **Relationship**

Each AE will be assessed as to its relationship to the investigational product, based on the following criteria. Although the attribution by the Investigator will be collected for reported events, for analytic purposes a temporal association with the use of the investigational product will be assumed sufficient for at least plausible association.

- Not related: No causal relationship exists between the investigational product and the AE, but an obvious alternative cause exists, e.g., the subject's underlying medical condition or concomitant therapy.
- Possibly related: A connection with the administration of the investigational product appears unlikely but cannot be ruled out with certainty. An AE may be considered possibly related if or when it meets 2 of the following criteria: (1) it follows a reasonable temporal sequence from administration of the investigational product; (2) it could not readily have been produced by the subject's clinical state, environmental or toxic factors, or other modes of therapy administered to the subject; or (3) it follows a known pattern of response to the investigational product.
- Related: There is a reasonable/plausible possibility that the AE may have been caused by the investigational product.

When assessing the relationship to the investigational product, the following criteria will be considered:

- Positive re-challenge (restart of IP dosing following dosing interruption);  
Note: In this study re-challenge of IP will not be allowed if IP dosing was discontinued for IP-related safety reasons e.g. when a DILI protocol is triggered and/or due to an AE that was assessed as possibly or probably related to the IP.
- Positive de-challenge (resolution upon stopping suspect the investigational product, in absence of other intervention or treatment);
- Known class effect;
- Biological plausibility; and
- Lack of alternative explanation—concomitant drug or disease.

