### **9.1 Definitions and Criteria**

#### **9.1.1 Adverse Events**

Per ICH E2A: An AE is any untoward medical occurrence in a subject or clinical investigation subject administered a pharmaceutical product and which does not necessarily have to have a causal relationship with this treatment. An AE can therefore be any unfavorable and unintended sign (including an abnormal laboratory finding, for example), symptom, or disease temporally associated with the use of a medicinal product, whether or not considered related to the medicinal product.

Medical interventions such as surgeries, diagnostic procedures, and therapeutic procedures are not AEs but the action taken to treat the medical condition. They should be recorded as treatment of the AEs.

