### **11.3.3 Safety Analysis**

#### **11.3.3.1 Adverse Events**

Adverse events will be coded by Preferred Term (PT) using the Medical Dictionary for Regulatory Activities (MedDRA) classification.

A treatment-emergent adverse event (TEAE) is defined as any AE that has an onset on or after the first dose of study drug, or any pre-existing condition that has worsened on or after the first dose of study drug. The incidence of TEAEs, treatment-related TEAEs, SAEs including deaths, TEAEs that lead to discontinuation of investigational product, and TEAEs by maximum severity and relationship to study drug will be summarized by MedDRA system organ class, PT, and treatment group.

To assess the potential for abuse associated with the administration of COR388 HCl, a systematic review of TEAE terms suggestive of the potential for abuse will be conducted for all clinical studies in subjects who received at least 1 dose of COR388 HCl and a summary of this information will be included in the regulatory submission. As a general framework for data collection and analysis we will use the overall abuse flag terms in the FDA Guidance (2017).

Since the target patient population are elderly, have substantial comorbidity and are often on other medications, a careful assessment and documentation of adverse event causality will be made in order to ensure that false positive TEAE signals for abuse are not generated. For example, dizziness and sedation or sleepiness are common clinical events in elderly patients with Alzheimer's disease.

Since to date no abuse related TEAE attributable to COR388 HCl have occurred, focus will be on a restricted set of index events for which narratives will only be prepared where the causality relationship to COR388 HCl is probable or definite. Information included in the narratives will consist of time to onset/offset, time course of severity, all concurrent events, concurrent medications, and time of onset of events relative to ingestion of COR388 HCl.

The index TEAEs will include:

- Any reports of altered perception or hallucinations
- Dizziness
- Euphoric mood
- Feeling drunk
- Feeling of relaxation
- Sedation
- Somnolence

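### The timing-only relationship rule in Protocol 9.1.5, if applied to the planned tables, makes the treatment-related TEAE summaries largely duplicate the all-TEAE summary

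*Protocol*

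**What the plan says.** The Relationship part of Protocol section 9.1.5 gives investigators three grades: *Not related*, *Possibly related* and *Related*. The middle grade carries a counting rule: "An AE may be considered possibly related if or when it meets 2 of the following criteria". Those criteria are a reasonable temporal sequence, the lack of a ready alternative explanation, and a known response pattern. The top grade reads: "There is a reasonable/plausible possibility that the AE may have been caused by the investigational product".

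The paragraph that introduces the grades separates what is recorded from what is analysed. It begins "Although the attribution by the Investigator will be collected for reported events" and continues "for analytic purposes a temporal association with the use of the investigational product will be assumed sufficient for at least plausible association".

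Section 11.3.3.1 defines a TEAE as "any AE that has an onset on or after the first dose of study drug", or a pre-existing condition that worsens from that point. It then lists the summaries by system organ class, preferred term and treatment group: "The incidence of TEAEs, treatment-related TEAEs, SAEs including deaths, TEAEs that lead to discontinuation of investigational product", followed by TEAEs by maximum severity and by relationship to study drug. It does not define treatment-related.

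**The concern.** The sentence in 9.1.5 is framed as a rule for analysis, and its opening concession sets the investigator's judgement aside for that purpose. It is the only relationship rule that the protocol states for analysis. A TEAE already satisfies a timing condition by construction, so a relationship rule that asks only for timing has little left to select on.

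At stake is what two planned safety tables mean. A programmer who follows 9.1.5 and one who uses the attribution on the eCRF would produce different treatment-related tables from the same data, and each could cite the protocol. Readers of the study report will look at related events, all the more because liver monitoring was increased on the DMC's recommendation during the trial.

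**Working it through.** The protocol states no figure on this point, so the check compares definitions.

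1. **Which events are TEAEs?** Under 11.3.3.1, any event that starts or worsens on or after the first dose. No end of window is given.

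2. **Which events are temporally associated with the product?** The protocol does not define this and gives no window. Section 9.1.1 already puts timing into its general wording on adverse events, which covers any "disease temporally associated with the use of a medicinal product, whether or not considered related to the medicinal product". On a plain reading, an event that starts during dosing qualifies.

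3. **What follows under the 9.1.5 rule?** Timing is enough for at least plausible association. Every TEAE that starts during dosing meets it, whatever the investigator recorded and whichever arm the subject is in.

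4. **Does that make it treatment-related?** Plausible association is not one of the three grades. The *Related* grade uses the same adjective, and sections 9.2.1 and 9.2.2 pair *Possibly related* with *Related* when they refer to events attributed to study treatment. If plausible association is read as belonging to that pair, *Not related* is nearly empty.

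5. **How much could a window separate the tables?** Suppose temporal association ends with the last dose. A completer is observed from Week 0 to Week 54 and dosed to Week 48, so the off-drug part is 54 − 48 = 6 weeks, or 6/54 = 11% of post-baseline follow-up. The share is larger for subjects who stop early. In an incidence table a subject drops out of the overall related count only if all of his or her TEAEs start in that off-drug part. The tables would therefore differ, but not by much among completers. A tighter window would separate them further; the protocol states none.

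6. **Is the rule consistent with the grades?** No.

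| Event with a temporal link only | Criteria met | Result |
|---|---|---|
| *Possibly related* grade, 9.1.5 | 1 of 3; 2 needed | Criteria not met |
| Analysis rule, 9.1.5 | Timing suffices | At least plausible association |

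7. **Are the grades used consistently elsewhere?** No. Section 11.3.3.1 selects abuse-potential narratives by *probable* or *definite* causality, and the re-challenge note in 9.1.5 refers to *possibly* or *probably* related events. *Probable* and *definite* are not on the three-level scale.

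**The case against.** The best defence is that the sentence is a caution, not a programming instruction: no TEAE should be dismissed because an investigator called it unrelated. Section 9 has relationship recorded on the eCRF for every adverse event, and relationship to study drug in 11.3.3.1 most naturally means that recorded variable. Section 11.1 leaves further detail to the SAP, and which grades count as treatment-related is ordinary SAP content.

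Much of this stands, and it rules out some stronger conclusions that a reader might draw:

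- **That every TEAE is related by definition and the two tables are identical.** This needs plausible association to be one of the formal grades, and any time after first dose to count as temporal association. The protocol states neither. An event late in the six-week follow-up is a TEAE but not clearly associated in time with use of a drug whose half-life at steady state is 4.5 to 5.0 hours.
- **That investigator attribution is never used.** Section 11.3.3.1 calls for careful causality assessment and selects the abuse-potential narratives by causality grade.
- **That the related rate would shift by a known amount.** The protocol gives neither a TEAE incidence nor an attribution rate.

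The defence does not remove the conflict. The sentence speaks of analytic purposes and subordinates the investigator's attribution. An SAP that used that attribution would override a stated rule, not fill a gap. The clash with the two-of-three criterion lies within one section and does not depend on the SAP.

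**Conclusion.** The point holds in conditional form. If the 9.1.5 rule is applied to the treatment-related and by-relationship tables, nearly every TEAE in every arm counts as at least plausibly related, and those tables largely duplicate the all-TEAE table. This rests on two assumptions: that plausible association is taken to mean *Possibly related* or *Related*, and that temporal association has no narrow window. Separately, and without either assumption, the rule conflicts with the criteria for *Possibly related*.

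The size of the effect on the related-TEAE rate cannot be given from the protocol. The consequence is small: all-TEAE incidence by arm is already planned and is the same under either reading, and no efficacy result, alpha level or interim rule depends on these tables. It is a wording correction worth making because it settles what a planned safety table reports.

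**What to change.** In 9.1.5, delete the temporal-association clause or limit it to the all-TEAE summaries. In 11.3.3.1, state that treatment-related TEAEs and the by-relationship tables use the investigator's recorded attribution, with *Possibly related* and *Related* counted as treatment-related, and that all-cause TEAEs by arm are the main safety comparison.

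At the same time, reconcile the grades named in the abuse-narrative paragraph of 11.3.3.1 and in the re-challenge note of 9.1.5 with the three-level scale, so that each refers to a grade that investigators can record. For the re-challenge note the need is only that the two passages agree; which clinical rule should apply is not a statistical question.

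The cost is about one sentence in each section, plus the alignment of grade names. The change to the tables needs no new data, because relationship is already recorded for each event.

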## 9.2 Reporting Procedures and Requirements

### 9.2.1 Adverse Events

Adverse events (AEs) occurring from when the subject signs the ICF until the last study event will be recorded. Any AEs occurring before the start of treatment (i.e., before the first dose of the investigational product) will be recorded in the medical

history. Also, the sign, symptom, or disease present before starting the treatment period are only considered AEs if they worsen after starting the treatment period.

If the Investigator detects an AE in a study subject after the last scheduled follow-up visit and considers the event possibly related or related to prior study treatment, the Investigator should report it to the Sponsor/ Contract Research Organization (CRO).

The Investigator should report all AEs on the AE page(s) of the eCRF and source documents, regardless of seriousness, severity, and causality. Whenever possible, an AE will be reported using a diagnostic term, (e.g., “common cold” or “upper respiratory infection” rather than “runny nose, cough, mild fever”) and should be described with the attributes described in [Section 9.1.5](#).

### **9.2.2 Serious Adverse Events**

Each AE will be assessed to determine whether it meets seriousness criteria ([Section 9.1.2](#)). If the AE is considered serious, the Investigator should report this event to the Sponsor and CRO as outlined below and also to the IRB/IEC according to its standard operating procedures.

If the Investigator detects an SAE in a study subject after the last scheduled follow-up visit, and considers the SAE related or possibly related to prior study treatment, the Investigator should report it to the Sponsor and CRO.

All information about SAEs will be collected and reported via the SAE form and sent by e-mail message or facsimile (contact information will be contained in the Investigator site file). The Investigator should send the initial report within 24 hours of becoming aware of the SAE. At minimum, the initial report should include the following information:

- Event;
- Study code;
- Subject number, initials, and date of birth;
- Investigational product; and
- Reporter name and contact information.

In the case of a “minimum report” (one that solely comprises the information bulleted above), a more detailed follow-up report should be sent as soon as more information becomes available, but no later than 7 calendar days after the date of the initial report. Each SAE should be followed up until resolution or stabilization and for reported deaths, the Investigator should supply Sponsor/ CRO and the IRB/IEC with any additional requested information (e.g., autopsy reports and terminal medical reports).

The original SAE form should be kept at the study site. The Sponsor or its representative will be responsible for determining and in turn, reporting SAEs to regulatory authorities according to the applicable regulatory requirements.

Serious adverse events that are ongoing at Safety Follow-up Visit 11 of OLE-9 should be followed until resolved or stabilized.

### **9.3 Procedures for Documenting Pregnancy During Study**

If a female subject becomes pregnant during the study, the Investigator will notify Sponsor/CRO immediately following 9.1.5 confirmation. The Investigator will also: (1) notify the subject's physician that the subject may have been treated with COR388 HCl and (2) follow the progress of the pregnancy to term and document the outcome of the pregnancy. Subjects who become pregnant during the study will not be eligible for any further study treatments. Pregnancy outcome information should be forwarded to Sponsor/CRO when available. The Investigator and Cortexyme will determine, on a case-by-case basis, whether the subject will continue in the study and, if so, which study measures will be collected.

### **9.4 Treatment of Investigational Product Overdose**

There is currently no information available regarding potential overdosing of COR388 HCl. Based on the effects observed in preclinical safety and toxicology studies, adverse effects that could be anticipated from exposure to overdoses of COR388 HCl are cardiovascular, CNS, and respiratory effects.

As there are no data available with regard to overdose of COR388 HCl in humans, there is no specific treatment to be used in the event of an overdose. Investigators should use their clinical judgment in treating cases of overdose as dictated by the subject's clinical status.

In the event of a suspected overdose, and if in the opinion of the Investigator the patient does not require emergency clinical treatment, the Investigator or treating physician should:

- Contact the Medical Monitor immediately.
- Have the subject come to the clinic as soon as possible to draw blood for clinical laboratory testing.
- Closely monitor the subject for AEs/SAEs and laboratory abnormalities and ensure appropriate clinical management. Overdose in the absence of other AEs will not be reported as an AE in its own right.
- Document the quantity of the excess dose, as well as the time of administration of the overdose, in the eCRF.
- Subjects should be observed closely in a medical facility where appropriate supportive care is available, if required.

## **10 QUALITY CONTROL AND QUALITY ASSURANCE**

### **10.1 Bioanalytic Method Validation**

Bioanalytic methods employed in this study have been validated according to existing standard operating procedures of the Sponsor and of the laboratory performing the analysis, in compliance with relevant regulation.

## **11 STATISTICAL AND ANALYTICAL PLANS**

### **11.1 General Considerations**

The statistical analyses are described in this section. Further details will be provided in the Statistical Analysis Plan (SAP), which will be finalized prior to database lock and unblinding for the interim analysis. Any deviations from the analyses described below will be included in the SAP.

All efficacy and safety measures over the course of the study will be presented. Continuous data will be summarized by means, standard deviations (SDs), medians, maximum, minimum, and number of subjects. Categorical data will be summarized by counts and percentages.

### **11.2 Determination of Sample Size**

The study will have an adaptive design that allows for potential adjustment in sample size and evaluation of efficacy based on the results of a planned interim analysis. An unblinded interim analysis will be conducted by a firewalled independent statistician (all clinical trial personnel will remain blinded) when approximately 100 subjects per arm have completed the Week 24 visit. Approximately 573 subjects are planned to be randomized 1:1:1 per treatment group (191 per treatment group) assuming approximately 10% will drop out prior to 48 weeks. Due to the planned interim analysis, adjustments will be made to the alpha level used in the final analysis to control for overall Type I error. The final criterion for efficacy to be used at the interim and final analysis depends on when the interim analysis occurs. The Lan-DeMets method modified according to [Chen et al. \(2004\)](#) to account for correlation between endpoints used at the interim and final analyses will be used to calculate the level of significance for each analysis. As originally planned, with 573 subjects randomized, an expected 10% discontinuation rate, and a single primary outcome, a total of 172 subjects per treatment group would provide approximately 90% power to detect a 2.5-point difference between the active treatment group compared to placebo with respect to change from baseline on the ADAS-Cog 11, assuming a standard deviation of 7.1, respectively at a significance level (alpha) of 0.05 using a two-sided test. The ADCS-ADL was added as a co-primary outcome, with assumptions of a 3.9-point difference between the active treatment group compared to placebo with respect to change from baseline on ADCS-ADL, assuming a standard deviation of 10.5, providing approximately 95% power on this outcome

measure, with approximately 90% power for the overall co-primary outcomes, depending on their correlation.

These results assume that 2 sequential tests will be made using the Lan-DeMets spending function to determine the test boundaries. Therefore, if an interim analysis is conducted when approximately 300 subjects have completed the Week 24 visit, then a significance level of 0.005 will be used for the interim analysis and a significance level of approximately 0.0456 will be used for the final analysis. As discussed by [Chen et al 2004](#), the sample size re-estimation procedure based on promising zone will not inflate the type I error and no statistical adjustment is necessary. However, the adjusted alpha at the end of the study will be based on the new sample size at the final analysis.

### **11.3 Final Analysis**

#### **11.3.1 Analysis Populations**

- **Intent-To-Treat Population (ITT):** The ITT population will include all subjects who are randomized regardless of whether or not they took study drug. This population will serve as the basis for all efficacy analyses. When change from baseline is assessed, subjects will be included in the analysis only if both a baseline and a postbaseline measure are available.
- **The Per Protocol population (PP):** The PP population will include all ITT subjects who do not have any major protocol deviations that would affect efficacy (e.g., <80% treatment compliance, taking a prohibited medication). Major protocol deviations will be reviewed and determined prior to unblinding. The PP population will be used for supportive sensitivity analyses.
- **Safety Population:** The Safety population will include all subjects who receive at least one dose of study drug. Safety analyses will be performed using the Safety population, and subjects will be analyzed according to the treatment they actually receive.

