#### 7.23 Allowances in the Circumstance of a Public Health Emergency

If an investigative site or the patients associated with that site experience a public health emergency, such as a pandemic, then throughout that time, the following changes to what is written elsewhere in this protocol are permissible at the discretion of the PI:

- **At-home and/or virtual visits:** Even when an investigative site remains open to clinical trial patients coming on site, social distancing strategies may result in some patients being unwilling or unable to attend protocol-specific clinic visits. For such reasons, scheduled clinic visits may be replaced by at-home or virtual visits. This may include visits by Study Site staff (or home healthcare providers, if applicable) or virtual visits by videoconference or telephone.
- **Safety assessments:** Every effort should be made to continue performing safety assessments on schedule. This may require visits by Study Site staff (or home healthcare providers, if applicable).

- **Transport of investigational product to support study drug administration:** It is permissible for study drug to be shipped directly to the patient and/or caregiver's home. It is also permissible for patients or caregivers to ship used study drug back to the site.
- **Visit windows:** For safety assessments, the visit windows will remain as given in [Table 1](#) and [Table 2](#), Schedule of Evaluations.
- **Testing at local laboratories:** If it is not practical to conduct testing on site using kits from the central laboratory, then it is permissible to use a local laboratory instead.

All instances when the above listed allowances are applied to the study conduct and its participants will be documented within the study source documents and reflected within the visit specific case report forms and protocol deviations log.

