#### **11.3.2.1.1 Sensitivity Analyses**

The following sensitivity analyses will be performed on each of the co-primary endpoints:

- Repeat above analysis using the PP population.
- Impute missing values using a last z-score carried forward method (converted back to the original scale) and analyze the primary endpoint (Average of Weeks 40 and 48 only) using analysis of covariance (ANCOVA) with fixed effects of treatment group, ApoE4 status, acetylcholinesterase inhibitor and/or memantine usage, site/country and baseline MMSE with baseline score as a covariate.
- Pattern mixture model:  
The pattern-mixture model approach uses a control-based pattern imputation ([Ratitch and O'Kelly, 2011](#)). With this approach, subjects who discontinued from the COR388 HCl 80 mg or COR388 HCl 40mg treatment group will be assumed to follow a similar outcome trajectory as subjects from the placebo (control) arm and subjects who discontinued from placebo (control) treatment are modeled as completers within their own arm (MAR within control arm). That is, the imputation model for the missing observations in the active treatment groups are constructed not from the observed data in the corresponding active treatment group but rather from the observed data in the placebo treatment group. This model is also the imputation model that will be used to impute missing observations in the placebo treatment group. This will

be implemented by utilizing the MONOTONE REG statement of SAS® PROC MI with the option nimpute=5.

Pattern mixture model tends to overestimate the already very large variability in Alzheimer's disease data, these model results are likely to be much less able to discriminate treatment differences than the primary model. The results of this imputation method will primarily be used to assess the potential bias of the main model estimates due to dropout by comparing the estimates between the primary and sensitivity models.

Additional subgroups including gender, demographic, and other baseline characteristics may be performed. Further details will be given in the SAP.

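### The post-baseline rule keeps the earliest dropouts out of both the primary MMRM and the control-based imputation, so comparing the two cannot show bias from losing them

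*Protocol*

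**What the plan says.** Protocol 11.3.1 defines the ITT population as all randomised subjects, dosed or not, and makes it the basis for every efficacy analysis. It then restricts change-from-baseline analyses: "subjects will be included in the analysis only if both a baseline and a postbaseline measure are available".

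Section 11.3.2.1 makes change from baseline in ADAS-Cog 11 and in ADCS-ADL (average of Weeks 40 and 48) the co-primary endpoints, analysed by MMRM. Section 11.3.2.1.1 lists sensitivity analyses for each of them. One is a control-based pattern-mixture model in which subjects who discontinue either active dose "will be assumed to follow a similar outcome trajectory as subjects from the placebo (control) arm", while placebo discontinuers are imputed as missing at random within placebo. It is to be carried out by "utilizing the MONOTONE REG statement" of SAS PROC MI. Its stated purpose is to gauge dropout bias in the main model by comparing the two sets of estimates. The section does not exempt this analysis from the rule in 11.3.1.

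After baseline, both scales are first scheduled at Visit 5 (Week 12). They are also collected at Early Termination (7.10, 8.6, 8.8), which 12.13 asks investigators to make every effort to complete.

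**The concern.** The control-based analysis asks what the treatment difference would be if people who left active drug went on to behave like placebo patients. The subjects for whom that matters most are those who left earliest, because they had least time on drug. Regression imputation can handle them, since a baseline score is enough to start the sequence.

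Under the rule in 11.3.1 they are never imputed. The primary MMRM does not contain them either, because a subject with no post-baseline record contributes nothing to it. The two estimates therefore share the same gap, and their agreement is no evidence about the effect of losing these subjects. If some early leavers have no score at all, the control-based estimate sits closer to the primary than it should, and the primary looks somewhat more robust than the data can show.

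**Working it through.** **Inputs from the protocol (11.2).** 573 randomised 1:1:1, 191 per arm; about 10% dropout before Week 48; ADAS-Cog 11 difference D = 2.5; SD 7.1; "at a significance level (alpha) of 0.05 using a two-sided test".

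**The plan's own figure first.** Evaluable per arm: 191 × 0.90 = 171.9, or 172. Standard error of the difference: 7.1 × √(2/172) = 0.766. Power: Φ(2.5/0.766 − 1.96) = Φ(1.31) = 0.904. The protocol says "a total of 172 subjects per treatment group would provide approximately 90% power", so its figure reproduces.

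**Assumed quantities, not in the protocol.** f is the share of active-arm dropouts with no post-baseline score, varied from 0 to 100%. r is the fraction of the effect kept by later dropouts, taken as 0 (full reversion to placebo) or 0.5. Subjects with no post-baseline score keep none of it.

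**Formulas.** Let d = 0.10. Placebo dropouts are imputed within their own arm and do not move the expected difference.

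- All randomised subjects with a baseline score: E_all = D × [(1 − d) + d(1 − f)r]
- With the 11.3.1 exclusion: E_excl = E_all / (1 − d·f)
- Understatement of the shift: E_excl − E_all

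**Results with r = 0.** E_all = 2.5 × 0.90 = 2.25, a true shift from 2.5 of 0.25 points. Expected dropouts per arm: 191 × 0.10 = 19.1.

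| f | Subjects per arm without a score | E_excl | Visible shift | Understated by |
|---|---|---|---|---|
| 0% | 0 | 2.25/1.000 = 2.250 | 0.250 | 0 |
| 12.5% | 2.4 | 2.25/0.9875 = 2.278 | 0.222 | 0.028 |
| 25% | 4.8 | 2.25/0.975 = 2.308 | 0.192 | 0.058 |
| 50% | 9.6 | 2.25/0.950 = 2.368 | 0.132 | 0.118 |
| 100% | 19.1 | 2.25/0.900 = 2.500 | 0 | 0.250 |

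The 25% row corresponds to uniform dropout over 48 weeks (12/48) with nobody who leaves before Week 12 attending Early Termination. The 12.5% row has half of them attending. The 50% row has no anchor in the protocol and is there to show the range.

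**Partial retention (r = 0.5).** At f = 25%: E_all = 2.5 × (0.90 + 0.0375) = 2.344, E_excl = 2.344/0.975 = 2.404, understated by 0.060. At f = 50%: 2.312 against 2.434, understated by 0.122. The choice of r hardly matters to the absolute figure.

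**Simulation check.** Sequential regression imputation from placebo was run with 400,000 per arm, assumed correlations and an effect growing linearly to 2.5 at Week 48. The difference averaged over Weeks 40 and 48 is then about 2.29. At d = 10% and f = 50% the control-based estimate was 2.11 with everyone and 2.22 with the exclusion, a gap of 0.11 and in line with the closed form.

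**Scale.** Understatements of 0.028, 0.058 and 0.118 are about 4%, 8% and 15% of the standard error of 0.766. If dropout were 20% or 30% (assumed), the upper limit would be 2.5 × 0.20 = 0.50 or 2.5 × 0.30 = 0.75 points.

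**The case against.** **The rule may not be meant to reach the imputed analysis.** Section 11.3.2.1.1 is the more specific text. It speaks of subjects who discontinued, without setting aside those with no later score, and the protocol does not say whether 11.3.1 applies before or after imputation. That is fair: this is the literal reading, not proof of intent. But the rule is general, no exception is stated, and a SAP that follows the text would inherit the exclusion.

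**Early Termination visits may capture these subjects.** Both scales are done there. Section 12.13 asks for every effort to obtain the visit, and requires the procedures for subjects who stop drug for drug-related safety reasons. This stands, and it is why the effect may be zero. It cannot cover everyone, since the same section lists death, withdrawal of consent and loss to follow-up as reasons for leaving.

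**The effect is small, and on a supportive analysis.** Also true.

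A reader might go further in two ways that the protocol does not support. The first is that the monotone routine's inability to take intermittent gaps also understates dropout bias. It has no fixed direction: filling on-drug gaps from placebo would pull the active arms towards placebo and widen the difference from the primary. Section 7.23 does foresee "some patients being unwilling or unable to attend protocol-specific clinic visits", but goes on to allow home or virtual visits in their place. A step that makes the data monotone is also detail the SAP, not shown here, may supply. The second is that this is the only check departing from missing at random. The same section also plans a last z-score carried forward analysis.

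**Conclusion.** The point holds in a limited form. On the protocol's literal text, dropouts with no post-baseline score are absent from both the primary MMRM and the control-based analysis, so the planned comparison cannot reveal bias from losing them. This does not show that the primary estimate is materially biased. At the planned effect and dropout, with full reversion to placebo, the 0.25-point shift is understated by about 0.03 to 0.12 points over assumed shares of 12.5% to 50%, by no more than 0.25 points, and by nothing if Early Termination captures everyone. The share without a score is not in the protocol and drives the result. It is worth correcting because the stated rule works against the analysis's stated purpose and the correction is nearly free.

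**What to change.** In 11.3.2.1.1, state that, as an exception to 11.3.1, the control-based imputation includes all randomised subjects with a baseline score and imputes from baseline where no post-baseline score exists. Carry the same sentence into the SAP.

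As a minor clarification, state that intermittent gaps in subjects still on drug are filled within their own arm under missing at random before the monotone regression step, so that placebo-based imputation applies only after discontinuation.

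The cost is two sentences and a few lines of code. The primary analysis, alpha and sample size do not change. The only downside is a slightly less favourable sensitivity estimate if early leavers without a score exist.
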